## 11.0 Specimen Collection and Banking (if applicable)

No specimens will be collected, banked, or analyzed specifically for this study. All clinical data, including laboratory results and biopsies, will be collected as part of usual care.

## 12.0 Data Management

Data capture will be accomplished using an electronic extraction and a study coordinator for manual chart abstraction. Data will be collected in a comprehensive longitudinal manner by review of the patient's electronic and paper medical records. Data collection will include all baseline donor/recipient demographics and transplant characteristics as well as longitudinal collection of medications, laboratory data and clinical events during

the post-transplant timeframe. The Research Electronic Data Capture (REDCap) system will be used for data management. REDCap is a secure, web-based application designed exclusively to support data capture for research studies. REDCap provides: 1) an intuitive interface for data entry (with data validation); 2) audit trails for tracking data manipulation and export procedures; 3) automated export procedures for seamless data downloads to common statistical packages (SPSS, SAS, Stata, R); 4) procedures for importing data from external sources; and 5) advanced features, such as branching logic and calculated fields. The REDCap project (<http://project-redcap.org/>) was initiated at Vanderbilt University and includes more than 70 active institutional partners from CTSA, GCRC, RCMC funded institutions, including MUSC, and others through a collaborative international consortium.

### **13.0 Provisions to Monitor the Data to Ensure the Safety of Subjects**

The terms adverse event (AE), serious adverse event (SAE), and adverse drug reaction (ADR), fatal, life threatening, disability, congenital anomaly, hospitalization, medically important, association with the use of drug, and unexpected adverse drug experience shall have the meaning as defined in 21CFR312.32, as detailed below.

Serious adverse event or serious suspected adverse reaction. An adverse event or suspected adverse reaction is considered "serious" if, in the view of either the investigator or sponsor, it results in any of the following outcomes: Death, a life-threatening adverse event, inpatient hospitalization or prolongation of existing hospitalization, a persistent or significant incapacity or substantial disruption of the ability to conduct normal life functions, or a congenital anomaly/birth defect. Important medical events that may not result in death, be life-threatening, or require hospitalization may be considered serious when, based upon appropriate medical judgment, they may jeopardize the patient or subject and may require medical or surgical intervention to prevent one of the outcomes listed in this definition. Examples of such medical events include allergic bronchospasm requiring intensive treatment in an emergency room or at home, blood dyscrasias or convulsions that do not result in inpatient hospitalization, or the development of drug dependency or drug abuse.

Suspected adverse reaction means any adverse event for which there is a reasonable possibility that the drug caused the adverse event. For the purposes of IND safety reporting, "reasonable possibility" means there is evidence to suggest a causal relationship between the drug and the adverse event. Suspected adverse reaction implies a lesser degree of certainty about causality than adverse reaction, which means any adverse event caused by a drug.

Unexpected adverse event or unexpected suspected adverse reaction. An adverse event or suspected adverse reaction is considered "unexpected" if it is not listed in the investigator brochure or is not listed at the specificity or severity that has been observed; or, if an investigator brochure is not required or available, is not consistent with the risk information described in the general investigational plan or elsewhere in the current application, as amended. For example, under this definition, hepatic necrosis would be unexpected (by virtue of greater severity) if the investigator brochure referred only to elevated hepatic enzymes or hepatitis. Similarly, cerebral thromboembolism and cerebral vasculitis would be unexpected (by virtue of greater specificity) if the investigator brochure listed only cerebral vascular accidents. "Unexpected," as used in this definition, also refers to adverse events or suspected adverse reactions that are mentioned in the investigator brochure as occurring with a class of drugs or as anticipated from the

pharmacological properties of the drug but are not specifically mentioned as occurring with the particular drug under investigation.

A Product Quality Issue (PQI) is defined as any defects related to the safety, identity, strength, quality, or purity of a medicinal product or with the physical characteristics, packaging, labeling, or design of a medicinal product.

Special Situation Report (SSR) is defined as any of the following events:

- Pregnancy: Any case in which a pregnant patient is exposed to a medicinal product or in which a female patient or female partner of a male patient becomes pregnant following treatment with a medicinal product. Exposure is considered either through maternal exposure or via semen following paternal exposure.
- Breastfeeding: Infant exposure from breast milk
- Overdose: Including any accidental or intentional overdose
- Drug abuse, misuse or medication error (potential or actual)
- Suspected (in the sense of confirmed or potential) transmission of an infectious agent: by a medicinal product.
- Lack of efficacy of a medicinal product
- Accidental exposure
- Use outside the terms of the marketing authorization, also known as “off-label” use
- Use of falsified medicinal product
- Unintended benefit

An SSR should be reported even if there is no associated AE.

### **Reporting Responsibilities:**

As the sponsor of the Study, MUSC and/or the PI shall be solely responsible for reporting any and all serious and unexpected adverse drug experiences or other safety information associated with the use of the Study Drug to the applicable Regulatory Authorities, the IRB or IECs and any Other Investigators, as required by applicable laws and regulations, including 21CFR312.32 within the timelines required, and whether or not the Study is being performed under an IND.

a) MUSC and/or the PI must notify TAKEDA or its designee within one (1) working day of becoming aware of a fatal or life-threatening SAE, within four (4) calendar days for other SAEs, and within seven (7) calendar days for all other events/issues listed above. This is achieved by submitting an AE Report Form to TAKEDA’s Pharmacovigilance Department to [[contact]](mailto:[contact]).

b) MUSC and/or the PI may be contacted by TAKEDA or its designee to obtain additional information on an adverse event or for data clarification. MUSC and/or the PI shall use its best efforts to obtain the requested additional information and will notify TAKEDA or its designee within one (1) working day of obtaining the additional information for a fatal or

life-threatening SAE, within four (4) calendar days for other SAEs, and within seven (7) calendar days for all other events/issues listed above.

c) MUSC and/or the PI agrees to update the Protocol and the informed consent at the request of TAKEDA for safety-related reasons.

#### **14.0 Withdrawal of Subjects**

Participation in this study is completely voluntary. Patients may withdraw at any time during the study. Treating physicians or providers may also request patients are withdrawn from the study if there are any safety concerns with participation. Patients that withdraw will be asked if they are willing to allow the data already collected on them to be included in analyses. Inclusion in the data analysis is also completely voluntary. If patients are agreeable, patient data will be censored at the time of withdrawal and these patients will be included in the intent-to-treat analyses.

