### 3. Recipient of investigational, non-FDA approved medication

#### 6.0 Number of Subjects

70 patients will be randomized 1:1 (35 in each arm) in blocks of 10. Once a patient is randomized and receives at least one dose of CMV prophylaxis medication they will be included in the study in an intent-to-treat manner. Those that are lost to follow-up, withdraw, or are taken off study drug will not be replaced.

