#### 10.0 Study Design / Methods

This will be a 12-month, single-center, open-label, randomized controlled clinical trial enrolling 70 total patients (35 in each arm). Given the limited sample size and single center design, this is a small, exploratory trial with limited power to detect significant differences between treatment arms for rates of CMV infection and other clinical endpoints (acute rejection, graft loss, death). The study is powered to detect clinically meaningful and statistically significant differences in the incidence of leukopenia accompanied by a reduce in total mycophenolate dose or valganciclovir dose (see power/sample size section). Patients will be randomly assigned to receive valganciclovir

900mg PO daily (this is considered standard usual care, adjusted for renal function) for 3-6 months post-transplant (based on CMV D/R serostatus as detailed below) or maribavir 400mg PO BID for 3-6 months post-transplant (based on CMV D/R serostatus as detailed below) + acyclovir 400mg PO BID for 1-month post-transplant (investigation arm, the addition of acyclovir to maribavir is considered standard usual care for HSV prophylaxis). Patients that are D+/R- will receive 6 months of prophylaxis, while all other CMV serostatuses will receive 3 months of prophylactic therapy (per MUSC usual care CMV protocol). All other medications, including immunosuppression and additional anti-infective prophylaxis, will be per standard usual care. All follow-up laboratory assessments and clinic visits will occur as per usual care as well. The only additional procedure specific to this study is that patients will be self-administered two surveys at 3, 6, and 12-months post-transplant, which can be completed online during a routine clinic visit or at home. There will be no visits conducted solely for this research study.

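### Section 14 lets a withdrawing patient keep outcomes already recorded out of the intent-to-treat analysis, which conflicts with section 6 and could tip a close result

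*Combined protocol and SAP*

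**What the plan says.** Section 14.0 (Withdrawal of Subjects) allows withdrawal throughout follow-up: "Patients may withdraw at any time during the study". Treating providers may also ask for a patient to be withdrawn over safety concerns. On data already in hand it says "Patients that withdraw will be asked if they are willing to allow the data already collected on them to be included in analyses", then "Inclusion in the data analysis is also completely voluntary", and then "If patients are agreeable, patient data will be censored at the time of withdrawal and these patients will be included in the intent-to-treat analyses".

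Section 6.0 (Number of Subjects) sets a different rule. Of patients who are randomised and receive at least one dose of prophylaxis, it says "they will be included in the study in an intent-to-treat manner", with no exception for patients who refuse use of their data. It adds: "Those that are lost to follow-up, withdraw, or are taken off study drug will not be replaced".

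Section 10.0 describes the trial as open-label with 35 patients per arm. Its Statistical Methods text gives no rule for counting or reporting refusals, no missing-data method, and no sensitivity analysis for patients left out.

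**The concern.** The two sections disagree on who is in the primary analysis set. Under section 6.0, a dosed patient who withdraws and refuses use of past data is in it. Under section 14.0, that patient is out.

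The difference matters because the choice comes after outcomes may be known. The primary endpoint is a low white-cell count with a dose reduction of mycophenolate or valganciclovir, which the patient may well be aware of. The patient also knows the assigned drug, and some of those asked will have been withdrawn for safety reasons. Ordinary loss to follow-up leaves earlier observations in place. This rule can take an observed event, and the patient who had it, out of a randomised comparison in which few events are expected.

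**Working it through.** **Inputs from the plan.** 35 per arm, 1:1 (section 6.0). Primary outcome yes/no per patient (section 4.0). Planned rates 33-35% on valganciclovir and 5-6% on maribavir, two-sided α=0.05, chi-square test, expected dropout or loss to follow-up 3-5% per arm (Power/Sample Size). Fisher's exact or Pearson's test as appropriate (Statistical Methods).

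**Plan's own figure.** The plan states 32 per arm for at least 80% power. The pooled-variance formula is

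n = [1.96·√(2p̄(1−p̄)) + 0.842·√(p₁(1−p₁)+p₂(1−p₂))]² / (p₁−p₂)²

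At 33% vs 6%, the least favourable pair, it gives 32.6, so 33 per arm; power at 32 is 0.792. The other corner pairs need 27 to 30. The stated figure is reproduced to within one patient per arm, and the point does not change the sample size.

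**How many patients.** 3% of 35 is 1.05 and 5% is 1.75, so about one or two per arm. This is an upper figure at the planned rate, because it includes patients lost to follow-up, who are not asked the section 14.0 question.

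**Expected events.** 35 × 0.35 = 12.25 on valganciclovir and 35 × 0.05 = 1.75 on maribavir: about 12 and 2.

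**Effect on single results.** Uncorrected Pearson test, χ² = N(ad−bc)² / (product of the four margins), 1 df:

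| Full data | p | After removal from analysis | p |
|---|---|---|---|
| 9/35 vs 3/35 | 0.057 | one maribavir event: 9/35 vs 2/34 | 0.024 |
| 10/35 vs 3/35 | 0.031 | two valganciclovir events: 8/33 vs 3/35 | 0.079 |
| 12/35 vs 2/35 | 0.003 | one maribavir event: 12/35 vs 1/34 | 0.0009 |
| 12/35 vs 2/35 | 0.003 | one valganciclovir event: 11/34 vs 2/35 | 0.005 |
| 12/35 vs 2/35 | 0.003 | two valganciclovir events: 10/33 vs 2/35 | 0.008 |

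(Valganciclovir is listed first.) For the first row, χ² = 70(9·32−26·3)²/(35·35·12·58) = 3.62 before removal, and 69(9·32−26·2)²/(35·34·11·58) = 5.06 after. Close results move, in either direction. A result near the planned effect does not.

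**Worst-case operating characteristics.** Sum the binomial probabilities of all pairs of counts (35 per arm) for which the Pearson test rejects after the stated removals. These figures assume that the removals happen in every trial, always involve event patients, and always fall in the named arm.

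- True rate 20% in both arms (assumed), with 0, 1 or 2 maribavir event patients removed: type I error 4.9%, 7.2%, 9.9%. The part favouring maribavir is 2.4%, 5.4%, 9.0%.
- True rate 35% in both arms, same removals: 5.2%, 5.8%, 7.6%.
- True rates 33% vs 6%, with 0, 1 or 2 valganciclovir event patients removed: power 0.86, 0.82, 0.74.

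**A milder scenario.** With a 20% true rate, suppose each maribavir event patient has a 5% chance (assumed) of withdrawing and refusing, and no valganciclovir patient does. Type I error is then 5.1% and the part favouring maribavir 3.0%. With 5% in both arms, type I error is 5.2%.

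**The case against.** The strongest reply is that the effect is small and conjectural. Few patients can be affected, and the plan gives no reason to expect those with leukopenia to refuse, or to refuse more often on one drug. The larger error rates treat removal as certain; the milder scenario barely moves them. Whether patients may exclude past data is also partly an ethical matter for the IRB, and the consent form is not among the documents reviewed. All of this stands, and it limits the size of the point. It does not settle the conflict between sections 6.0 and 14.0 or supply a rule for handling refusals.

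Four stronger readings are tempting, and the documents do not support them.

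- **The data are erased.** Section 14.0 governs inclusion in analyses. It says nothing about destroying records, and the safety-reporting duties in section 13.0 carry no exception for withdrawn patients.
- **The whole comparison becomes self-selected.** Only withdrawn patients who refuse are affected.
- **Any single removal changes the answer.** At 12/35 vs 2/35 it does not. The example also depends on the test: 10/35 vs 3/35 becoming 10/35 vs 2/34 crosses 0.05 under Fisher (0.062 to 0.023) but not under Pearson (0.031 to 0.013). The smallest expected count there is 35 × 13/70 = 6.5, so Pearson would be the usual choice.
- **Removal will depend on arm and outcome, in maribavir's favour.** It could, because the trial is open-label. Neither the dependence nor its direction is known.

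**Conclusion.** The point holds in a limited form. Followed as written, section 14.0 can exclude observed primary events from the intent-to-treat analysis at the patient's choice, contrary to section 6.0, and nothing else in the plan resolves this. At the planned dropout rate the practical risk is confined to close results. The rises in type I error to 7.2% or 9.9%, and the fall in power to 0.74, are upper illustrations and not forecasts. The number, arm and event status of refusers are assumptions, since the documents give none. It should still be corrected: the change is cheap, and once a patient has refused, the analysis cannot use the excluded outcome.

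**What to change.** Amend section 14.0, and the consent wording to match, so that data collected up to withdrawal stay in the intent-to-treat analysis and withdrawal stops further collection only. This brings section 14.0 into line with section 6.0.

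If the IRB requires a refusal option:

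- keep refusers in the randomised denominator;
- report the number of refusals by arm;
- add a sensitivity analysis that counts maribavir refusers as events and valganciclovir refusers as non-events, plus the reverse. In the first example above, counting the one maribavir refuser as an event returns 9/35 vs 3/35, p=0.057, and shows that the result is fragile.

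The cost is protocol and consent wording with IRB approval. No extra patients or visits are needed, and the sample size is unchanged. The small downside of the main fix is that participants lose the option to exclude past data from analysis.

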#### **15.0 Risks to Subjects**

As both maribavir and valganciclovir are FDA approved for the treatment of CMV infection, comparison of these therapies to prevent CMV infection (prophylaxis) in solid organ transplant recipients is not expected to induce undue harm or risk. There is the potential that either maribavir or valganciclovir prophylactic therapy may lead to reduced or improved safety and/or efficacy in preventing CMV infection; however, this has yet to be proven in the context of CMV prophylaxis in kidney transplant recipients. Thus, there is sufficient equipoise to conduct this clinical trial. Patients and outcomes will be closely monitored in both treatment arms during the conduct of this study. Given the small sample size, interim analyses will not be conducted unless requested by Takeda Pharmaceuticals or the MUSC IRB.

#### **16.0 Potential Benefits to Subjects or Others**

Given previous data, there is a strong possibility that those randomized to the maribavir arm will have similar efficacy with regards to preventing CMV infection, as compared to valganciclovir while also having lower rates of leukopenia that leads to reductions in mycophenolate dosing and/or valganciclovir therapy.

#### **17.0 Sharing of Results with Subjects**

[figure not shown]
Results will be shared with participants after the study is complete. We will share results by updating the clinicaltrials.gov website with outcomes data and sharing the site with patients enrolled in the study. We will also share results to healthcare providers through presentation at transplant conferences and publication in peer reviewed journals.

#### **18.0 Drugs or Devices**

Valganciclovir is considered current gold-standard therapy to prevent CMV infection in transplant recipients. Those randomized to valganciclovir will receive it through usual care processes. The prescription will be filled by the Rutledge Tower Pharmacy or a pharmacy of the patient's choice and it will be billed to the patient's insurance. The patient will be responsible for any copays related to valganciclovir prophylactic therapy. Those randomized to the maribavir arm will receive both the maribavir and acyclovir through the study, dispensed by the MUSC Investigational Drug Services (IDS) at no charge to the patient. The research study coordinator will ensure the patient receives these medications, either by hand delivery to the patient or through mailing the medications to the patient.

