## 1.0 Objectives / Specific Aims

- Aim 1. Assess the incidence of leukopenia in those randomized to maribavir vs. valganciclovir prophylaxis in adult kidney transplant recipients at high-risk of CMV infection.
  - Hypothesis 1. The incidence of clinically meaningful leukopenia, defined as a WBC count of  $< 3,000$  cells/mm^3 and a reduction in total mycophenolate dose below 1,500 mg/day or valganciclovir dose below 900mg per day (adjusted for renal function), will be significantly lower in the maribavir arm, as compared to the valganciclovir arm.
- Aim 2. Assess the efficacy of maribavir vs. valganciclovir prophylaxis in adult kidney transplant recipients at high-risk of CMV infection.
  - Hypothesis 2. The incidence of CMV infection and disease will be similar between the maribavir arm, as compared to the valganciclovir arm, at 3-, 6-, and 12-months post-transplant.
- Aim 3. Assess the impact of maribavir vs. valganciclovir prophylaxis on healthcare utilization and costs in adult kidney transplant recipients at high-risk of CMV infection.
  - Hypothesis 3. Healthcare utilization will be lower in the maribavir arm, as compared to the valganciclovir arm, at 6- and 12-months post-transplant, driven predominantly by reduced number of telephone calls, televisits, and laboratory monitoring encounters.
- Exploratory Aim 4. Assess the impact of maribavir vs. valganciclovir prophylaxis in adult kidney transplant recipients at high-risk of CMV infection on patient-reported outcomes for quality of life and satisfaction.
- Exploratory Aim 5. Assess any differences in leukopenia, efficacy, healthcare utilization and patient reported outcomes by race and sex in patients randomized to maribavir vs. valganciclovir prophylaxis in adult kidney transplant recipients at high-risk of CMV infection.

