4. Valganciclovir dose reduction (Secondary Outcome) – Defined as a reduction in dose of  $<900$ mg per day (adjusted for renal function. This will be assessed as a dichotomous outcome (yes/no) per patient as well as a rate (number of unique valganciclovir dose reduction events per patient-year). Events will be considered unique once the valganciclovir dose is returned to full dose for at least one week. The length of time a patient has their valganciclovir dose reduced and the severity of dose reduction (nadir dose) will also be assessed. This endpoint will be measures at 3-, 6-, and 12-months post-transplant.
5. CMV prophylaxis drug dose adjustment or discontinuation (Secondary Outcome) – Defined as a reduction in dose, holding or discontinuation of the maribavir or valganciclovir therapy. This will be assessed as a dichotomous outcome (yes/no) per patient as well as a rate (number of unique dose adjustment events per patient-year). Events will be considered unique once the CMV prophylaxis drug dose is returned to full dose for at least one week. The length of time a patient has their CMV prophylaxis drug dose reduced or held and the severity of dose reduction (nadir dose) will also be assessed. This endpoint will be measures at 3- and 6-months post-transplant.
6. Acute Rejection (Secondary Outcome) - defined as a renal allograft biopsy demonstrating at least grade 1A rejection by Banff criteria. We will also record and assess all borderline acute rejections and antibody mediated rejections using the most current Banff classification system. All patients will be required to have biopsy confirmation of rejection episodes, as per usual care and the MUSC clinical protocol. It is standard care that all kidney allograft biopsies performed for transplant recipients occur at the transplant center (study institution). Biopsies will be read by the local pathologist, as usual care. The study coordinator capturing clinical event data will review the medical record to determine the timing, severity, treatment regimen and reversibility of each acute rejection episode for all patients in the study.
7. Hospitalizations (Secondary Outcome) – Defined as any admission to a hospital with at least one overnight stay. All-cause hospitalization will be assessed for this study. Hospitalizations due to CMV and other infections will be sub-analyzed as well.

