### **Efficacy Measures**

10. CMV Infection (Secondary Outcome) – defined as detectable CMV in the patient's plasma. Currently, MUSC uses CMV DNA PCR (plasma IU/mL) to assess for infection with nucleic acid amplification techniques that are calibrated to the WHO international standard for human CMV. The lower level of detection is 50 IU/mL. Per the MUSC CMV protocol and usual care (see Appendix), any level >1,000 IU/mL will be considered CMV infection for the purposes of this study. All cases of CMV infection, regardless of the presence or absence of symptoms, will be classified as infection. CMV DNA PCR is measured at MUSC per our protocol using event-driven criteria, which includes either leukopenia or symptoms consistent with CMV infection (N/V/D, anorexia, fever, chills, and/or malaise). For the purposes of this study, the reason for measuring CMV DNA PCR will be captured and analyzed as well. Further, MUSC usual care CMV protocol suggests measuring CMV DNA PCR in those that are D+/R- after prophylaxis is discontinued (post-transplant month 7, 9 and 12). The protocol also recommends measuring CMV DNA PCR at month 4, 7, and 12 after discontinuation of antiviral prophylaxis in moderate risk patients (R+, see Appendix). CMV symptoms and treatment will also be recorded. Late CMV infection will be defined based on occurrence of first CMV infection after completion of CMV prophylaxis (3- or 6-months post-transplant). These endpoints will be assessed at 3-, 6-, and 12-months post-transplant. Breakthrough cases of CMV infection, defined as the presence of CMV DNA while on anti-CMV prophylaxis, will also be assessed.
11. CMV Disease (Secondary Outcome) – defined as the presence of organ dysfunction in the setting of CMV infection with biopsy proven presence of CMV in the affected organ, done at MUSC using DNA hybridization. This will be sub-classified by organ type; most common in kidney transplant recipients will be CMV gastrointestinal disease, CMV pneumonia, or CMV nephritis. Less common include CMV hepatitis, CMV retinitis, CMV encephalitis, CMV cystitis, CMV myocarditis, and CMV pancreatitis. Late CMV disease will be defined based on occurrence of first CMV infection after completion of CMV prophylaxis (3- or 6-months post-transplant). This endpoint will be assessed at 3-, 6-, and 12-months post-transplant. Breakthrough cases of CMV disease will also be assessed.

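### Drug supply differs by arm and interruptions are recorded without a reason, so item 5 and the CMV comparison can mix drug effect with access

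*Combined protocol and SAP*

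**What the plan says.** Section 18.0 (Drugs or Devices) describes two supply routes.

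- **Valganciclovir** comes through usual care, from the center's own pharmacy or any other that the patient picks, with the bill going to insurance. On cost: "The patient will be responsible for any copays related to valganciclovir prophylactic therapy". No check that the patient has the drug in hand is described.
- **Maribavir and acyclovir** are "dispensed by the MUSC Investigational Drug Services (IDS) at no charge to the patient", and "The research study coordinator will ensure the patient receives these medications", by hand or by mail.

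Section 4.0, Safety Measures, item 5 is a secondary outcome: "Defined as a reduction in dose, holding or discontinuation of the maribavir or valganciclovir therapy". It attaches no reason to the event. It is analysed as yes/no per patient and as a rate, at 3 and 6 months. The Statistical Methods list prophylaxis interruption among the key outcomes to be compared between arms by chi-square or Fisher's exact test.

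Under Efficacy Measures, CMV infection (item 10) is defined by viral load alone. Breakthrough infection is "defined as the presence of CMV DNA while on anti-CMV prophylaxis, will also be assessed". Hypothesis 2 expects CMV infection and disease to be similar in the two arms.

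Item 16 counts telephone calls at the study center as healthcare utilization, split by encounter type and provider type. Hypothesis 3 expects lower utilization on maribavir, "driven predominantly by reduced number of telephone calls, televisits, and laboratory monitoring encounters".

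The data collection list and assessment table in section 10.0 include antiviral doses. They list no fill record, adherence measure or reason for an interruption.

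**The concern.** The trial is open-label, and the arms differ in the drug and also in how the drug reaches the patient: price, pharmacy route and coordinator support all follow randomization. A patient who runs out of valganciclovir because of a copay or an insurance delay has an interruption that says nothing about tolerability. Item 5 as worded can still take it in as a safety outcome.

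The CMV comparison is exposed in a more awkward direction. If some valganciclovir patients go without drug for reasons of access and then develop CMV, the comparator looks less effective. Under a hypothesis of similarity, extra comparator failures make maribavir look similar even if it protects less well. In an arm of 35, one patient is 1/35 = 2.9 percentage points. An infection during an unrecorded gap could also be filed as breakthrough on prophylaxis.

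Unless the reason for a gap is written down at the time, the two effects may not be separable afterwards.

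**Working it through.** **Plan's own figure.** The plan gives no rate of supply gaps or of item 5 events, so there is none to reproduce on this point. The nearest stated figure, 32 per arm for the primary endpoint, serves as a check on the method.

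Formula: n per arm = [1.96 √(2p̄(1−p̄)) + 0.842 √(p1(1−p1) + p2(1−p2))]² / (p1−p2)².

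With the least favorable stated rates, 33% against 6%, p̄ = 0.195:

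[1.96 × √0.31395 + 0.842 × √0.2775]² / 0.27² ≈ 2.376 / 0.0729 ≈ 32.6, so 33 per arm.

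The plan states 32. Power at 32 per arm is 0.792 (plan: 0.809). The agreement is close enough to use the same normal approximation below.

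**Illustration 1: item 5.** Inputs: 35 per arm (section 6.0) and two-sided α = 0.05 (Power/Sample Size). Assumed, because the documents give neither:

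- a clinical interruption rate r, the same in both arms;
- a supply-gap rate g in the valganciclovir arm only, with every gap recorded as an event.

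The last assumption is deliberately extreme. The valganciclovir rate becomes p1 = 1 − (1−r)(1−g). The chance of significance against valganciclovir is 1 − Φ[(1.96·SE0 − d)/SE1], where

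- d = p1 − r and p̄ = (p1 + r)/2;
- SE0 = √(2p̄(1−p̄)/35);
- SE1 = √([p1(1−p1) + r(1−r)]/35).

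Worked case, r = 10% and g = 10%: p1 = 1 − 0.9 × 0.9 = 0.19, d = 0.09, SE0 = 0.0842, SE1 = 0.0835; (0.1650 − 0.09)/0.0835 = 0.898; chance = 18.5%.

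| r, both arms | g, valganciclovir only | Valganciclovir rate | Difference (points) | Chance of significance against valganciclovir |
|---|---|---|---|---|
| 10% | 5% | 14.5% | 4.5 | 8.2% |
| 10% | 10% | 19% | 9 | 18.5% |
| 10% | 20% | 28% | 18 | 48.3% |
| 20% | 5% | 24% | 4 | 6.0% |
| 20% | 10% | 28% | 8 | 11.9% |
| 20% | 20% | 36% | 16 | 31.7% |
| 30% | 5% | 33.5% | 3.5 | 5.0% |
| 30% | 10% | 37% | 7 | 9.0% |
| 30% | 20% | 44% | 14 | 22.5% |

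With no gaps the one-directional chance is about 2.5%. Fisher's exact test, which the plan also allows, would give lower values. Gaps in the maribavir arm, or gaps that never reach the chart, would shrink the differences.

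**Illustration 2: primary endpoint.** Suppose a fraction g of valganciclovir patients lose enough exposure to have the maribavir-arm leukopenia risk. The valganciclovir rate is then 0.35(1−g) + 0.05g.

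| g | Valganciclovir rate | Power, 35 per arm, against 5% |
|---|---|---|
| 0 | 35% | 0.898 |
| 5% | 33.5% | 0.873 |
| 10% | 32% | 0.844 |
| 20% | 29% | 0.774 |

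Here the supply effect works against the maribavir hypothesis. One route runs the other way: a gap coinciding with a low white cell count might be read as meeting the valganciclovir-dose part of the definition.

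**The case against.** The strongest reply is that usual-care supply of valganciclovir is a deliberate choice in a trial that adds no visits, that antiviral doses are assessed at the same scheduled times in both arms, and that the affected endpoints are secondary in a trial that calls itself exploratory with limited power for CMV infection. This stands as an argument against changing how the control drug is supplied. It does not answer the missing reason field, because the other arm does not get usual-care supply.

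It is also fair that item 5's language of nadir dose and return to full dose suits prescribed dosing at least as well as dispensing gaps. The documents do not say how an unfilled prescription is coded, and chart abstraction may miss gaps at outside pharmacies. This limits how many gaps would be counted. It also shows that the plan needs a rule.

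Several stronger readings are tempting and are not supported:

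- *Supply gaps count against valganciclovir only.* Item 5 names both drugs, and mailed maribavir can arrive late.
- *Item 4 is affected in the same way.* Item 4 covers dose reductions; holds and discontinuations appear only in item 5.
- *Telephone calls are inflated in one arm.* Other medications are usual care in both arms, so supply calls can arise in both. Calls to insurers or outside pharmacies are not center encounters. Delivery contacts for maribavir may or may not be counted.
- *Every outcome leans towards maribavir.* Missed valganciclovir could lower leukopenia in the control arm, and with it the laboratory tests and calls behind Hypothesis 3.
- *Supply-driven item 5 events can be compared with about 12 leukopenia events (35% of 35).* That is the primary-endpoint rate, which the plan supports with mycophenolate reductions. It is not an item 5 rate.

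**Conclusion.** The point holds in a limited form. Cost, pharmacy route and assured receipt differ by arm, so access-related gaps are more likely with valganciclovir. Item 5 ignores the reason for an interruption, and the CMV endpoints come with no record of whether drug was in hand. The item 5 comparison and the Hypothesis 2 conclusion can therefore mix a drug effect with a supply effect.

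The size is unknown. The 5-8%, 9-19% and 23-48% chances of a spurious item 5 finding rest on assumed gap rates of 5%, 10% and 20% in one arm only, all recorded, with equal clinical interruption of 10-30%. They show sensitivity and do not estimate the bias. For the primary endpoint the likelier direction is against maribavir. The effect on telephone calls is possible but its direction is unsettled. Nothing here changes the sample size.

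**What to change.** 1. In the existing chart abstraction, record prospectively and in both arms the reason for each prophylaxis interruption: toxicity or intolerance, including stops initiated by the patient; other clinical reason; supply, insurance or cost; other.
2. Keep item 5 as defined. Add a prespecified sensitivity analysis that excludes only supply-, insurance- or cost-driven interruptions. Do not restrict the endpoint to prescriber-directed changes, because that would drop patients who stop a drug themselves for intolerance.
3. Report supply gaps by arm beside the CMV infection and disease results.
4. Where the chart shows why a telephone call was made, repeat the item 16 comparison with drug-supply and study-logistics calls excluded in both arms.

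This extends what the plan already does when it captures the reason for each CMV PCR and the cause of each ED visit. The cost is modest extra abstraction for 70 patients, with no copay funding and no added visits. Capture of gaps at outside pharmacies will be incomplete, and the report should say so. A coordinator receipt check for valganciclovir as well is an option, but it would move the control arm away from usual care and leave the copay difference in place, so it is not part of this recommendation.
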